## **7.5        SECONDARY ENDPOINT(S)**

### **7.5.1      Key secondary endpoint(s)**

This section is not applicable, as no key secondary endpoint has been specified in the protocol.

### **7.5.2      Secondary endpoint**

*The secondary endpoint [...] AUC0-∞ will be calculated according to the relevant BI internal procedures. and will be assessed statistically using the same methods as described for the primary endpoints.*

## **Safety and tolerability endpoints**

Refer to [Section 7.8](#) for a description of the analysis of safety and tolerability.

## **7.7        EXTENT OF EXPOSURE**

Descriptive statistics are planned for this section of the report based on the TS. The date and time of drug administrations will be listed for each subject.

## **7.8        SAFETY ANALYSIS**

All safety analyses will be performed on the TS.

The safety data for treated subjects who failed to complete the study (dropouts or withdrawals) will be reported as far as their data are available. All withdrawals will be documented and the reason for withdrawal recorded.

## 7.8.1 Adverse Events

Unless otherwise specified, the analyses of AEs will be descriptive in nature. All analyses of AEs will be based on the number of subjects with AEs and NOT on the number of AEs. BI standards as presented in “Analysis and Presentation of Adverse Event Data from Clinical Trials – Display Template” [BI-KMED-BDS-HTG-0041] (9) and [BI-KMED-BDS-HTG-0066] (10) will be applied.

The analysis of AEs will be based on the concept of treatment emergent AEs. That means that all AEs will be assigned to ‘screening’, ‘on-treatment’ or ‘follow-up’ phases as defined in [Section 6.1](#). AEs will be analysed based on actual treatments, as defined in [Table 6.1: 1](#).

According to the CTP, adverse events of special interest (AESI) will be analysed:

**Section 5.2.6.1.4 of the CTP:** *The following are considered as AESIs:*

- Hepatic injury

*A hepatic injury is defined by*

- o ALT and/or AST  $\geq 8$  fold ULN*
- o ALT and/or AST  $\geq 3$  fold ULN and total bilirubin  $\geq 2$  fold ULN\**
- o ALT and/or AST  $\geq 3$  fold ULN and unexplained INR  $> 1,5$ \**
- o ALT and/or AST  $\geq 3$  fold ULN and unexplained eosinophilia ( $> 5\%$ )\**
- o ALT and/or AST  $\geq 3$  fold ULN and appearance of fatigue, nausea, vomiting, right upper abdominal quadrant pain or tenderness, fever and/or rash*

*\* in the same blood draw sample.*

According to ICH E3 (11), in addition to deaths and serious adverse events, ‘other significant’ AEs need to be listed in the clinical trial report. These will be any non-serious adverse event that led to an action taken with study drug (e.g. discontinuation or dose reduced or interrupted).

An overall summary of AEs will be presented.

The frequency of subjects with AEs will be summarised by treatment, primary system organ class (SOC) and preferred term (PT). Separate tables will be provided for subjects with serious AEs, for subjects with drug-related AEs, for subjects with drug-related serious adverse events and for subjects with AESIs. In addition, the frequency of subjects with AEs will be summarised by treatment, worst intensity, primary SOC and PT.

The SOCs and PTs will be sorted by frequency (within SOC). The MedDRA version number will be displayed as a footnote in the respective output.

In addition, frequencies of subjects with non-serious AEs that had an incidence of  $> 5\%$  for at least one treatment will be summarised by treatment, primary SOC and PT.

For disclosure of adverse events on EudraCT, additional information not included in a standard AE analysis will be performed. The following three entries will be created:

- Adverse Events per arm for disclosure on EudraCT
- Non-serious Adverse Events for disclosure on EudraCT
- Serious Adverse Events for disclosure on EudraCT

### **7.8.2      Laboratory data**

The analyses of laboratory data will be descriptive in nature and will be based on BI standards [BI-KMED-BDS-HTG-0042] ([12](#)).

Laboratory data will be analysed qualitatively via comparison of laboratory data to their reference ranges. Values outside the reference range as well as values defined as possibly clinically significant will be flagged in the data listings.

Clinically relevant findings in laboratory data will be reported as baseline conditions (at screening) or as AEs (during the trial) if judged clinically relevant by the investigator, and will be analysed as such.

It is the investigator's responsibility to decide whether a lab value is clinically significantly abnormal or not (at the RPM at the latest).

Descriptive statistics of laboratory data including change from baseline will be calculated by planned time point based on the worst value of the subject at that planned time point (or assigned to that planned time point).

### **7.8.3      Vital signs**

Vital signs (blood pressure and pulse rate) will only be listed.

Clinically relevant findings in vital signs will be reported as AEs.

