7. STATISTICAL METHODS AND DETERMINATION OF SAMPLE SIZE

7.1 STATISTICAL DESIGN – MODEL

The main objective of this trial is to investigate the relative bioavailability of 100 mg nintedanib given as 4 capsules à 25 mg (Test, T) compared with 100 mg nintedanib given as 1 capsule à 100 mg (Reference, R) following oral administration on the basis of the primary and secondary pharmacokinetic endpoints, as listed in Section [2.1.2](#) and [2.1.3](#). The trial is designed to allow intra-subject comparisons and will be evaluated statistically by use of a linear model for logarithmically transformed PK endpoints.

The assessment of safety and tolerability is a further objective of this trial, and will be evaluated by descriptive statistics for the parameters specified in Section [2.2.2.2](#).

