7.3.4 Safety analyses

Safety will be analysed based on the assessments described in Section [2.2.2.2](#). All treated subjects (TS, refer to Section [7.2](#)) will be included in the safety analysis. Safety analyses will be descriptive in nature and based on BI standards. No hypothesis testing is planned.

For all analyses, the treatment actually administered (= treatment at onset) to the subject will be used (any deviations from the randomised treatment will be discussed in the minutes of the Report Planning Meeting).

Treatments will be compared in a descriptive way. Tabulations of frequencies/proportions will be used to evaluate categorical (qualitative) data, and tabulations of descriptive statistics will be used to analyse continuous (quantitative) data.

Measurements (such as ECG, vital signs, or laboratory parameters) or AEs will be assigned to treatments (see Section [4.1](#)) based on the actual treatment at the planned time of the measurement or on the recorded time of AE onset (concept of treatment emergent AEs). Therefore, measurements planned or AEs recorded prior to first intake of trial medication will be assigned to the screening period, and those between trial medication intake and end of REP (see Section [1.2.1](#)) will be assigned to the respective treatment period. Events occurring after the REP but prior to next intake or end of trial termination date will be assigned to 'follow-up'. In case of two or more treatments, the follow-up will be summarized according to the previous treatment. These assignments including the corresponding time intervals will be defined in detail in the TSAP. Note that AEs occurring after the last per protocol contact but entered before final database lock will be reported to Pharmacovigilance only and will not be captured in the trial database.

Additionally, further treatment intervals (analysing treatments) may be defined in the TSAP in order to provide summary statistics for time intervals, such as combined treatments, on-treatment totals, or periods without treatment effects (such as screening and follow-up intervals).

Adverse events will be coded using the Medical Dictionary for Regulatory Activities (MedDRA). Frequency, severity, and causal relationship of AEs will be tabulated by treatment, system organ class, and preferred term. SAEs, AESIs (see Section [5.2.6.1](#)), and other significant AEs (according to ICH E3) will be listed separately.

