Previous and concomitant therapies will be presented per treatment group without consideration of time intervals and treatment periods.

Laboratory data will be compared to their reference ranges. Values outside the reference range as well as values defined as possibly clinically significant will be highlighted in the listings. Additionally, differences from baseline will be evaluated.

Vital signs or other safety-relevant data will be assessed with regard to possible on-treatment changes from baseline.

Relevant ECG findings will be reported as AEs.

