#### **4. CHANGES IN THE PLANNED ANALYSIS OF THE STUDY**

All analyses as planned in the CTP will be performed and are described in more detail in this TSAP.

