## 6.7 BASELINE, TIME WINDOWS AND CALCULATED VISITS

The baseline value is defined as the last measurement before administration of nintedanib in each treatment period.

**Section 6.1 of the CTP:** *The acceptable time windows for screening, study measurements and assessments scheduled to occur 'before' trial medication administration on Day 1, and the end of trial examination are provided in the CTP Flow Chart.*

*If not stated otherwise in the Study Protocol Flow Chart, the acceptable deviation from the scheduled time for laboratory tests will be  $\pm 2$  h.*

*For planned blood sampling times, refer to the CTP Flow Chart. Starting from planned time of 48 hours after drug administration (and beyond) a time window of +/- 120 minutes will be allowed for all procedures.*

Adherence to time windows will be checked via the consistency check listings at the RPM.

Unscheduled measurements of laboratory data and vital signs data will be assumed to be repeat measurements of the most recent scheduled measurement (e.g. for follow-up or confirmation of a particular value). Therefore, unscheduled measurements will be assigned to the planned time point of the previous scheduled measurement.

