## **7. PLANNED ANALYSIS**

Safety analysis (refer to [Section 7.8](#)) will be performed by [REDACTED] and will be presented in Sections 15.1 to 15.4 of the CTR and in Appendix 16.2 and 16.1.13.1.

Inferential statistical analyses of PK endpoints (refer to [Section 7.4](#) and [Section 7.5.2](#)) will also be performed by [REDACTED] and will be presented in Section 15.5 of the CTR and in Appendix 16.1.13.3.

Descriptive data analysis of PK endpoints and concentrations will be performed by the department of [REDACTED] at [REDACTED] and will be presented in Section 15.6 of the CTR.

The format of the listings and tables will follow the BI standards with the exception of those generated for PK-calculations following BI standards for PK/PD analysis ([7](#)).

The individual values of all subjects will be listed, sorted by treatment sequence, subject number and visit. The listings will be included in Appendix 16.2 of the CTR.

For end-of-text tables, the set of summary statistics for non-PK parameters is:

N	number non-missing observations
Mean	arithmetic mean
SD	standard deviation
Min	minimum
Median	median
Max	maximum

For analyte concentrations, the following descriptive statistics will additionally be calculated:

CV	arithmetic coefficient of variation
gMean	geometric mean
gCV	geometric coefficient of variation

For PK parameters, the following descriptive statistics will additionally be calculated:

CV	arithmetic coefficient of variation
gMean	geometric mean
gCV	geometric coefficient of variation
P10	10th percentile
Q1	1st quartile
Q3	3rd quartile
P90	90th percentile

The data format for descriptive statistics of concentrations will be identical to the data format of the respective concentrations. The descriptive statistics of PK parameters will be calculated using the individual values with the number of decimal places as provided by the evaluation program. Then the individual values as well as the descriptive statistics will be reported with three significant digits in the CTR.

Tabulations of frequencies for categorical data will include all possible categories and will display the number of observations in a category as well as the percentage (%) relative to the respective treatment group (unless otherwise specified, all subjects in the respective subject set whether they have non-missing values or not).

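### SAP 7.8.3 reduces vital signs to a listing, although the protocol plans descriptive tables and a change-from-baseline assessment and SAP Section 4 declares no change

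*SAP*

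**What the plan says.** **Protocol.** Section 2.2.2.2 names vital signs (blood pressure and pulse rate) among the safety and tolerability parameters. Section 7.1 says that safety and tolerability "will be evaluated by descriptive statistics for the parameters specified in Section" 2.2.2.2. Section 7.3.4 adds that treatments will be compared descriptively and that "tabulations of descriptive statistics will be used to analyse continuous (quantitative) data". It then turns to vital signs in particular: "Vital signs or other safety-relevant data will be assessed with regard to possible on-treatment changes from baseline".

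**SAP.** Section 7.8.3 says "Vital signs (blood pressure and pulse rate) will only be listed", and adds that clinically relevant findings will be reported as adverse events. No other section supplies a vital-signs summary. Section 4, where departures from the protocol would be declared, says "All analyses as planned in the CTP will be performed and are described in more detail in this TSAP".

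The SAP also holds what a summary would need. Section 6.7 states "The baseline value is defined as the last measurement before administration of nintedanib in each treatment period", and for laboratory and vital signs data it says that "unscheduled measurements will be assigned to the planned time point of the previous scheduled measurement". Section 7 lists the statistics for end-of-text tables, introduced by "the set of summary statistics for non-PK parameters is": N, mean, SD, minimum, median and maximum.

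**The concern.** The SAP is meant to elaborate the protocol's analysis. For vital signs it removes part of that analysis while stating that nothing has been removed. The word *only* in SAP 7.8.3 means that the section cannot be read as silent and left to the general rules.

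At stake is a planned descriptive output for a named safety endpoint. A listing of individual values shows neither the average level of blood pressure or pulse rate under each treatment nor the average change from the period's baseline. Reporting relevant findings as adverse events captures the individual abnormalities that the investigator judges important, but not a modest shift across the group. A reader of the trial report who relied on SAP Section 4 would expect the protocol's vital-signs summary and not find it.

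**Working it through.** No power, alpha or sample-size figure is involved, so the check is a comparison of the two documents, followed by a count of what is missing.

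**Step 1: does the protocol commit to a summary?** The vital-signs sentence in Section 7.3.4 requires an assessment of change from baseline but does not itself say table. Two other statements settle the form. Section 7.1 ties descriptive statistics to every parameter in Section 2.2.2.2, vital signs included. Section 7.3.4 prescribes tabulated descriptive statistics for continuous safety data, and blood pressure and pulse rate are continuous. Read together, these plan tabulated statistics and a look at change from baseline.

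**Step 2: does the SAP carry it through?** Section 7.3.4 gives a separate instruction for each of three classes of measurement.

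| Class | Protocol 7.3.4 | SAP | Carried through |
|---|---|---|---|
| Laboratory | Compare with reference ranges; evaluate differences from baseline | 7.8.2: both, with change from baseline by planned time point | Yes |
| ECG | Report relevant findings as adverse events | 7.8.4: same | Yes |
| Vital signs | Assess on-treatment change from baseline | 7.8.3: listing, with relevant findings as adverse events | No |

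So 1 of the 3 classes is not carried through. The per-period baseline and the time-point rule in SAP 6.7 feed the laboratory summary, but no planned vital-signs summary uses them.

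**Step 3: does SAP Section 4 declare the difference?** No. It says that all protocol analyses will be performed.

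**Step 4: how much output is missing?** Inputs: 3 parameters (systolic pressure, diastolic pressure, pulse rate), 2 treatments (T and R), the 6 statistics of SAP Section 7, and 2 quantities (value and change). Per post-baseline time point:

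3 × 2 × 6 × 2 = 72 table cells, against 0 planned.

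This figure only illustrates the size of a standard table. The number of post-dose time points could not be confirmed, because the flow chart columns are shifted in the text available for this review. Marks at 6, 12, 24, 34, 48 and 72 h could belong either to vital signs or to adverse-event questioning. The range is therefore 0 to 6 post-dose time points in each treatment period, or 0 to 6 × 72 = 432 cells. The protocol's own flow chart should settle this. The contradiction in Steps 1 to 3 does not depend on it.

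**The case against.** The strongest reply has four parts.

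- **The specific sentence promises no table.** It names no statistic and no time point. Listed values, together with adverse-event reporting of relevant changes, could be called an assessment. Taken alone, that sentence allows this reading. Taken with Section 7.1 and the tabulation rule in 7.3.4 it does not, because a listing contains no descriptive statistics and no comparison of treatments.
- **The general rule would also catch ECG.** If Section 7.1 binds every parameter in 2.2.2.2, ECG should have statistics too, and SAP 7.8.4 gives none. But 7.3.4 has its own ECG sentence sending relevant findings to adverse events, and the SAP follows it. For vital signs the specific sentence points to change from baseline, and the SAP does not follow it. The 1-of-3 count should be read in that limited sense.
- **Sponsor standards and the role of the statistics list.** Section 7.3.4 also refers to internal standards that are not available here, and the six statistics apply where a table is produced; they do not order one. Both statements are correct. However, the protocol sets out tabulation and change from baseline alongside those standards, and SAP 7.8.3 cites no standard in support of a listing alone.
- **There may be little to tabulate.** If the doubtful flow chart marks are adverse-event questioning, scheduled vital signs are limited to screening, pre-dose and the end-of-trial visit on Day 8 to 14. That visit falls at or after the end of the 7-day (168 h) on-treatment phase. The table would then be short and would hold few or no on-treatment values. This bears on the size of the loss and cannot be excluded. It does not make the statement in SAP Section 4 correct.

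**Conclusion.** The concern holds: SAP 7.8.3 contradicts protocol 7.1 and 7.3.4, and SAP Section 4 is inaccurate for vital signs. This is a stated rule that conflicts with the protocol, not a missing detail.

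The severity is minor. All 3 vital-sign parameters get 0 of the 6 standard statistics, for values and for change from baseline. The loss is confined to descriptive safety output: SAP Section 7 still lists all individual values, SAP 7.8.1 tabulates adverse events, and the relative bioavailability results are unaffected.

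The conclusion rests on reading protocol 7.1 and 7.3.4 together as planning tabulated statistics for vital signs. Confidence in the textual conflict is high. The practical size of the missing table is uncertain until the scheduled times are read from the flow chart.

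**What to change.** In SAP 7.8.3, keep the listing and add a table of N, mean, SD, minimum, median and maximum for systolic pressure, diastolic pressure and pulse rate, and for their change from the SAP 6.7 period baseline. Present it by treatment and by the planned times at which the flow chart schedules vital signs, on the treated set. SAP Section 4 would then be true for vital signs.

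The cost is one standard table from data already collected. The baseline, the handling of unscheduled values and the statistics are already defined in the SAP.

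If the sponsor intends a listing alone, the alternative is to record that in SAP Section 4 as a change from the protocol, with the reason. That would remove the inconsistency but not supply the summary the protocol planned.

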### **7.8.4      ECG**

ECG recordings will be checked by the investigator for pathological results. Clinically relevant abnormal findings for ECG will be listed under 'Relevant Medical History / Baseline Conditions' (when they occurred during screening) or will be reported as AEs (when they occurred during treatment), and will be analysed as such.

No separate ECG listing will be provided.

**7.8.5      Others**

Physical examination

Physical examination findings will be reported as relevant medical history/baseline condition (i.e., a condition already existent before intake of study drug) or as AE and will be summarised as such.

[figure not shown]
No separate listing or analysis of physical examination findings will be prepared.

## **8. TIMEPOINT OF RELEASE OF TREATMENT INFORMATION**

The treatment information will be loaded into the trial database after completion of enrolment, i.e. the randomisation has been completed.

## **11. HISTORY TABLE**

Table 11: 1 History table

Version	Date (DD-MMM- YY)	Author	Sections changed	Brief description of change
1	29-SEP-21		None	This is the final TSAP
